## **3 STUDY IMPLEMENTATION**

### **3.1 STUDY DESIGN**

This is a randomized, prospective pilot study of TARP peptide vaccination in HLA-A\*201 patients with Stage D0 prostate cancer. HLA-A\*201 positive eligible patients with *no evidence*

of brain, visceral or bony metastatic disease, a non-castrate testosterone level  $\geq 50$  ng/dL (prior ADT allowed; must be  $\geq 6$  months since last dose of ADT), and a PSADT  $> 3$  months and  $\leq 15$  months will be randomized to receive TARP peptides with Montanide® ISA 51 VG adjuvant plus GM-CSF administered by deep subcutaneous (SC) injection or autologous, TARP peptide-pulsed dendritic cells administered intradermally (ID).

TARP peptides or TARP-pulsed dendritic cells will be administered every three weeks at weeks 3, 6, 9, 12, and 15 for a total of five vaccinations with a booster dose of TARP vaccine given at Weeks 48 and 96. PSADT will be calculated in months at the following study time points: Pre-Enrollment/Baseline, weeks 12, 24, 36, 48, 60, 72, 84, 96, 108, 120, 132, and 144. PSADT will be calculated using the Memorial Sloan-Kettering Cancer Center cancer information prostate nomogram for PSA doubling time found at:

<http://www.mskcc.org/mskcc/shared/forms/Nomograms/flash/load.cfm?type=Prostate&width=586&height=505&title=Prostate%20Nomogram> as recommended in the Prostate Specific Antigen Working Group Guidelines. Cumulative PSA values within 12 months inclusive of the study time point will be used for calculation of the baseline/Week 0 PSADT.

Exploratory comparisons of percent change in PSADT will be done among the following time points:

[figure not shown]
- Pre-Enrollment/Baseline PSADT vs. Week 12 PSADT
- Pre-Enrollment/Baseline PSADT vs. Week 24 PSADT
- Pre-Enrollment/Baseline PSADT vs. Week 36 PSADT
- Pre-Enrollment/Baseline PSADT vs. Week 48 PSADT
- Week 24 PSADT vs. Week 36 PSADT
- Week 36 PSADT vs. Week 48 PSADT
- Additional exploratory analyses of PSADT will be performed of Pre-Enrollment/Baseline PSADT vs. Weeks 60, 72 and 96 and Week 48 PSADT vs. Weeks 96, 108 and 144 PSADT.

Week 24 PSADT responders will be allowed to receive an additional dose of TARP peptide vaccine at Week 36. All patients will receive a booster of vaccine at Weeks 48 and 96.

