**3.5 CONCURRENT THERAPIES**

3.5.1 Contraindicated Therapies

3.5.1.1 Patients may not receive chemotherapy, hormonal therapy or radiation therapy while on study.

3.5.1.2 Systemic administration of steroids is not allowed with the exception of oral corticosteroids for management of acute allergic reactions or contact hypersensitivity of  $\leq 14$  days duration in patients who require them. Topical steroids as well as intranasal steroids are permitted. Patients must not have received systemic steroids within 14 days to TARP peptide vaccination.

3.5.1.3 Pharmacologic doses of immune modulating agents including IVIG, recombinant cytokines or growth factors.

3.5.1.4 Immunosuppressive agents such as cytotoxic chemotherapy.

3.5.1.5 Other investigational agents.

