## 3.6 CRITERIA FOR REMOVAL FROM PROTOCOL THERAPY AND OFF STUDY CRITERIA

### 3.6.1 Criteria for removal from protocol therapy

- 3.6.1.1 Patient experiences a Grade 3 or greater toxicity attributed as possibly, probably or definitely related to vaccine as described in Section 3.3 Treatment Modifications and Immunization Stopping Rules.
- 3.6.1.2 Patient is taken off treatment by the Principal Investigator or Lead Associate Investigator for reasons other than toxicity e.g. insufficient recovery of dendritic cells to generate required vaccine dose, failure to adhere to scheduled study visits, etc.

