### 3.6.3 Off Study Criteria

- 3.6.3.1 Patient elects to withdraw from participation in the study at any time.
- 3.6.3.2 Patient is removed from study after resolution of Grade 3 or greater toxicities attributed as possibly, probably or definitely related to vaccine as described in Section 3.3 Treatment Modifications and Immunization Stopping Rules.
- 3.6.3.3 Patient develops evidence of brain, visceral or bony metastatic disease.
- 3.6.3.4 Patients with a calculated PSADT that has *decreased* by  $\geq 50\%$  compared to their Pre-Enrollment/Baseline PSADT. PSADT is calculated as specified in Section 3.1.
- 3.6.3.5 Patients with a calculated PSADT of  $\leq 3$  months at any of the outlined PSADT assessment time points i.e. weeks 12, 24, 36 or 48. PSADT is calculated as specified in Section 3.1.
- 3.6.3.6 For those patients receiving them, a discontinuation or dose reduction of their Flomax or 5-alpha reductase inhibitors.
- 3.6.3.7 Patient completed study

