### 5.2.2 PSADT Response Criteria

PSADT was chosen as a surrogate marker for biochemical response to vaccination based on the Prostate-Specific Antigen Working Group's consensus Guidelines on PSADT. Utilization of PSADT as a predictive factor of disease progression and prostate cancer death is based on level II evidence derived from cohort- or case-controlled analytic studies or controlled, non-randomized trials that have been validated in multiple data sets, PSADT will be calculated using the Memorial Sloan-Kettering Cancer Center cancer information prostate nomogram for PSA doubling time found at:

<http://www.mskcc.org/mskcc/shared/forms/Nomograms/flash/load.cfm?type=Prostate&width=586&height=505&title=Prostate%20Nomogram> recommended in the Prostate Specific Antigen Working Group Guidelines. The PSADT is calculated assuming an exponential increase in serum PSA and first order kinetics. The formula takes into account the natural logarithm of 2 divided by the slope obtained from fitting a linear regression of the natural log of PSA on time. All PSA values used in the calculation should be 0.20 ng/ml or greater and follow an increasing trend. PSA values need not be consecutively increasing and all values obtained during a maximum period of 12 months prior to a given protocol time point will be included in the calculation. The maximum period of the last 12 months is recommended to reflect current disease activity because in some men PSADT may change over time. Multiple studies concur that men with a PSADT < 3 months are at extremely high risk for metastatic disease progression

and death with prostate cancer mortality approaching 100%; for this reason they have been excluded from participation in this study. In contrast, men with a slow PSADT i.e. > 15 months have an extremely low risk of death from prostate cancer.

The following general guidelines regarding PSA determinations and calculation of PSADT used in this protocol will be adhered to (refer to [Appendix 5](#), PSADT Calculation Guidelines)

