#### **Pre-Enrollment/Baseline and On Study PSADT:**

- PSADT will be calculated using the Memorial Sloan-Kettering Cancer Center cancer information prostate nomogram for PSA doubling time found at:  
<http://www.mskcc.org/mskcc/shared/forms/Nomograms/flash/load.cfm?type=Prostate&width=586&height=505&title=Prostate%20Nomogram>
- Minimum requirements for PSADT include  $\geq 3$  PSA measurements over  $\geq 3$  months.
- The interval between PSA measurements must be  $\geq 4$  weeks.
- For patients receiving 5-alpha reductase inhibitors (5ARI) e.g. finasteride or dutasteride, only PSA values obtained after at least 3 months on therapy may be used to calculate PSADT.
- Calculated PSADT values will be reported in months
- The same laboratory must have performed PSA values used in the calculation of PSADT.
- All PSA values used in the calculation should be  $\geq 0.20$  ng/mL and follow a rising trend although all values need not be consecutively rising.
- All values obtained over a maximum period of 12 months prior to any given protocol time point assessment should be included in the PSADT calculation to reflect the patient's current disease activity.
- PSA values obtained within  $\leq 2$  weeks of instrumentation, documented infection (prostatitis), or radiation proctopathy should be *omitted* from inclusion in PSADT calculations.

On Study PSADT will be calculated at baseline and weeks 12, 24, 36, 48, 60, 72, 84, 96, 108, 120, 132, and 144.

Exploratory comparisons of percent change in PSADT will be done among the following time points:

- Pre-Enrollment/Baseline PSADT vs. Week 3-12 PSADT/
- Pre-Enrollment/Baseline PSADT vs. Week 24 PSADT
- Pre-Enrollment/Baseline PSADT vs. Week 36 PSADT
- Pre-Enrollment/Baseline PSADT vs. Week 48 PSADT
- Week 24 PSADT vs. Week 36 PSADT
- Week 36 PSADT vs. Week 48 PSADT
- Additional exploratory analyses of PSADT will be performed of Pre-Enrollment/Baseline PSADT vs. Weeks 60, 72 and 96 and Week 48 PSADT vs. Weeks 96, 108 and 144 PSADT.

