#### **5.2.2.1 PSADT Response & Failure**

**(assessed in all patients at weeks 12, 24, 36, 48, 60, 72, 84, 96, 108, 120, 132, and 144.)**

- PSADT *response* is defined as:
  - a  $\geq 50\%$  increase in calculated PSADT OR

- a PSADT > 15 months
- Patient's whose PSADT is *decreased* by  $\geq 50\%$  will be considered PSADT *failures*.
- Week 24 PSADT *responders* will be allowed to receive an additional dose of TARP peptide vaccine at Week 36.

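### Off-study rule 3.6.3.5 (PSADT of 3 months or less) stops at week 48, leaving a narrow group of men with no mandatory PSADT exit in weeks 60 to 144

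*Combined protocol and SAP*

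**What the plan says.** Two off-study criteria in Section 3.6.3 use PSADT.

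- 3.6.3.5 sets an absolute floor. A man leaves if his PSADT is 3 months or less "at any of the outlined PSADT assessment time points i.e. weeks 12, 24, 36 or 48".
- 3.6.3.4 is relative. A man leaves if his PSADT has fallen by at least 50% "compared to their Pre-Enrollment/Baseline PSADT". It lists no weeks.

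Both refer to Section 3.1 for the calculation. Section 3.1 schedules on-study PSADT from week 12 to week 144. Section 5.2.2.1 has response and failure "assessed in all patients at weeks 12, 24, 36, 48, 60, 72, 84, 96, 108, 120, 132, and 144". Section 5.2.2 fixes the window for each calculation: "All values obtained over a maximum period of 12 months prior to any given protocol time point assessment should be included".

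The reason for the 3-month floor is in Section 5.2.2: "men with a PSADT < 3 months are at extremely high risk for metastatic disease progression", and such men are kept out at entry. Criterion 2.1.1.3.7 admits baseline PSADT above 3 and up to 15 months.

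On treatment after week 48, Section 3.1 states: "All patients will receive a booster of vaccine at Weeks 48 and 96". The notes to Appendix 1 make the extension to week 144 elective. Section 3.5.1.1 states: "Patients may not receive chemotherapy, hormonal therapy or radiation therapy while on study".

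**The concern.** The opening words of 3.6.3.5 suggest every scheduled PSADT assessment, but the abbreviation *i.e.* then restricts them to four weeks. The list may be left over from a 48-week schedule. As written, though, it decides who must leave.

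The protocol treats a PSADT under 3 months as too dangerous for entry and applies that floor on study up to week 48. It gives no reason for lifting the floor for the following 96 weeks. A man whose disease accelerates in that period may have no PSADT rule that takes him off study, may not have hormonal or radiation therapy while he stays, and is due another vaccine dose at week 96. What is at stake is patient protection and uniform handling of exits: staff who follow the general phrase and staff who follow the list would treat the same man differently.

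**Working it through.** The plan states no figure to reproduce here. The check sets the two rules against each other and then follows one assumed patient.

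**1. Time points.** On-study PSADT (3.1, 5.2.2.1): weeks 12, 24, 36, 48, 60, 72, 84, 96, 108, 120, 132, 144, which is 12. Listed in 3.6.3.5: 4. Unlisted: 12 − 4 = 8, of which 7 (weeks 60 to 132) come before the final visit.

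**2. The uncovered band.** Let B be baseline PSADT and P the on-study value.

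- 3.6.3.4 applies when (B − P)/B ≥ 0.5, that is P ≤ B/2.
- 3.6.3.5 applies when P ≤ 3, at weeks 12 to 48 only.
- After week 48 a man is below the floor but not removed when B/2 < P ≤ 3. This needs B/2 < 3, so B < 6. Entry requires B > 3.
- Width of the band: 3 − B/2.

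| B (months) | Uncovered P (months) | Width |
|---|---|---|
| 3.5 | above 1.75, up to 3.0 | 1.25 |
| 4 | above 2.0, up to 3.0 | 1.0 |
| 5 | above 2.5, up to 3.0 | 0.5 |
| 6 or more | none | 0 |

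Since B > 3, the width is always below 3 − 1.5 = 1.5 months. A grid search in 0.05-month steps gave the same limits: the band exists for B from 3.05 to 5.95 and is empty at 6.

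**3. Worked case (assumed values).** PSA doubles every 4.0 months to week 48 and every 2.5 months afterwards, without noise. PSADT is ln 2 divided by the slope of ln PSA on time, using scheduled PSA visits in the previous 52 weeks; 1 week = 7/30.4375 = 0.22998 month.

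From week 24 visits are 12 weeks apart, or 12 × 0.22998 = 2.760 months. PSA therefore rises by 2.760/4.0 = 0.690 doublings per interval before week 48 and 2.760/2.5 = 1.104 after it. For five equally spaced visits the slope is Σxy/10 with x = −2, −1, 0, 1, 2 and y in doublings relative to week 48.

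- Week 72 (visits 24 to 72): y = −1.380, −0.690, 0, 1.104, 2.208. Slope = (2.760 + 0.690 + 0 + 1.104 + 4.416)/10 = 0.897. PSADT = 2.760/0.897 = 3.08.
- Week 84 (visits 36 to 84): y = −0.690, 0, 1.104, 2.208, 3.312. Slope = (1.380 + 0 + 0 + 2.208 + 6.624)/10 = 1.021. PSADT = 2.760/1.021 = 2.70.

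The same regression gives 4.0 at week 48, 3.65 at week 60 (3.59 if visits are thinned to at least 4 weeks apart) and 2.50 from week 96. The 3.6.3.4 limit is 4.0/2 = 2.0 and is never reached. With all time points in 3.6.3.5 he leaves at week 84, before the week 96 booster. As written, no PSADT rule removes him in the remaining 144 − 84 = 60 weeks.

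**4. When the floor is first reached.** Eight assumed cases (baseline to PSADT after week 48, in months), each with acceleration starting at week 48:

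- Week 72: 3.5 to 2.0, 3.5 to 2.5, 4 to 2.25.
- Week 84: 4 to 2.5, 4 to 2.75, 5 to 2.6.
- Week 96: 5 to 2.75, 5.5 to 2.8.

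The last two cross at the booster visit itself, so the order of assessment and dosing matters.

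**The case against.** Several other provisions protect this man. The extension is elective and he may withdraw at any time (3.6.3.1). Section 3.6.1.2 covers discretionary removal: "Patient is taken off treatment by the Principal Investigator or Lead Associate Investigator for reasons other than toxicity". CT and bone scans are scheduled at weeks 96 and 144, with restaging in between if clinically indicated (3.4.3), and metastatic disease found there can trigger 3.6.3.3, which has no week limit. PSA and clinical review continue every 12 weeks.

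In the worked case PSA would be conspicuous. By week 84 it has doubled 48 × 0.22998/4.0 + 36 × 0.22998/2.5 = 2.76 + 3.31 = 6.07 times, about 67-fold over week 0. By week 96 it has doubled 2.76 + 4.42 = 7.18 times, about 145-fold. Someone would probably act.

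All of this stands, and it is why the point is minor. It does not make the rule right. Discretion under 3.6.1.2 ends treatment, not study participation, so the bar on other therapy in 3.5.1.1 remains. The scans detect metastasis, whereas the 3-month floor exists to act on the risk of it.

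The eight cases show timing only. A reader might note that 3.6.3.4 applies in none of them and infer that the gap is common. It could not apply: each case was given a PSADT above half of baseline throughout. The documents give no event rates.

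**Conclusion.** The concern holds as an internal inconsistency with a small patient-protection consequence. After week 48 there is no mandatory PSADT exit for men with baseline above 3 and below 6 months whose PSADT is above half of baseline and at or below 3 months. The band follows from the text alone. The timings rest on assumed, noise-free doubling times that change at week 48. Severity is minor.

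Three stronger readings are not supported:

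- A reader might infer that no PSADT rule operates after week 48. Criterion 3.6.3.4 does, and it removes every man at or below half of baseline, hence every man at or below 3 months whose baseline was 6 or more.
- A reader might infer that an affected man stays unmonitored to week 144. The safeguards above say otherwise; only the mandatory PSADT trigger is missing.
- A reader might infer a similar gap for nodal spread, because 3.6.3.3 names brain, visceral or bony disease while 2.1.1.3.3 bars any metastatic disease. The text does not say whether nodes count as visceral, so this is at most a matter of clarification.

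No number of affected patients and no effect on the primary immunologic endpoint is claimed.

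**What to change.** In 3.6.3.5, replace the *i.e.* clause and its four weeks with *listed in Section 3.1*. This ties the rule to the schedule it already cites and leaves no B/2 < P ≤ 3 case uncovered. Add that the rule is assessed before any vaccine dose at that visit, and that the immune sample already scheduled for the visit is taken before the man leaves. If the week 48 limit is intended, the sponsor should say so and give the reason.

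The change needs no new visits, scans or assays. PSADT would have to be known before dosing at visits where both fall due, such as week 96.

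The real cost is lost late data. Sections 3.1 and 3.4.4 list 11 post-baseline immune time points (weeks 12, 18, 24, 36, 48, 60, 96, 108, 120, 132, 144). An exit at weeks 60 to 84, with the sample scheduled for that visit taken, loses 5 of the 11: weeks 96, 108, 120, 132 and 144. Because Section 5.2.1 requires a positive assay to be confirmed at two time points, the loss could occasionally include a confirming sample.

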### 3.6.4 Off-Study Procedure

Authorized staff must notify Central Registration Office (CRO) when a subject is taken off-study. An off-study form from the web site (<http://home.ccr.cancer.gov/intra/eligibility/welcome.htm>) main page must be completed and faxed to [contact].

## **4 SUPPORTIVE CARE**

We do not anticipate significant systemic or organ toxicities associated with TARP peptide vaccination using either Montanide® ISA 51 VG plus GM-CSF or peptide- pulsed dendritic cells. We have not observed any clinically significant toxicities in our previous trials investigating other class I peptides in patients with lung or colon cancer. Non-steroidal anti-inflammatory medication or other analgesics and possibly antihistamines may be needed for local injection site reactions to vaccination.

## **5 DATA COLLECTION AND EVALUATION**

### **5.1 DATA COLLECTION**

The Vaccine Branch clinical research team will perform real time data collection. The Principal Investigator will be responsible for oversight of the protocol.

All patients enrolled on study will be centrally registered at the NCI Central Registration Office. All on study evaluations must be performed within one week of their scheduled time point as outlined in the study schema ([Appendix 1](#)). Delay in vaccine administration is allowed for up to 3 weeks as outlined in Section [3.3.3](#). Modifications in this policy can be discussed on an individual basis with the Lead Associate Investigator. Research data will be collected in the NCI C3D database.

All AEs, including clinically significant abnormal findings on laboratory evaluations, regardless of severity, will be followed until satisfactory resolution. AEs should be reported up to 30 days following the last dose of study drug.

An abnormal laboratory value will be considered an AE if the laboratory abnormality is characterized by any of the following:

- Results in discontinuation from the study
- Is associated with clinical signs or symptoms
- Requires treatment or any other therapeutic intervention
- Is associated with death or another serious adverse event, including hospitalization.
- Is judged by the Investigator to be of significant clinical impact

**End of study procedures:** Data will be stored according to HHS, FDA regulations, and NIH Intramural Records Retention Schedule as applicable.

**Loss or destruction of data:** Should we become aware that a major breach in our plan to protect subject confidentiality and trial data has occurred, the IRB will be notified.

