### 3.4.1 Clinical Evaluation

(weeks 0, 3, 6, 9, 12, 15, 18, 24, 36, 48, 60, 72, 84, 96, 108, 120, 132 and 144.)

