## **7 SAFETY REPORTING REQUIREMENTS/DATA AND SAFETY MONITORING PLAN**

At each study visit, patients will be evaluated for new or evolving AEs. Symptoms will be elicited through the use of open-ended questions, followed by appropriate questions that clarify the patient's verbatim description of AEs or changes in concomitant medications. A review of systems will be performed.

The Principal Investigator or Lead Associate Investigator will assess whether the AE or SAE is associated with the administration of TARP peptide vaccine:

- Unrelated, Unlikely, Possible, Probably, Definite

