### 9.3.6 Reported Adverse Events and Potential Risks

Common adverse events reported with peptides emulsified with Montanide® ISA 51 VG have consisted of fatigue, fever, flushing, injection site reactions including pain, erythema and induration; localized swelling, rare granuloma formation. Other reported possible adverse events include chills/rigors, transient increases in liver transaminases, headache, rash, and pruritis. TARP is a 58 amino acid protein found on cells of prostate origin and is over expressed in over 90% of patients with prostate cancer and about half of patients with breast cancer. Because the peptide mimics portions of a prostate protein found naturally in the body, there is a chance for development of an autoimmune reaction to it and may result in the possible development of inflammation in the prostate gland.

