HIV Serology								
Hepatitis B Serology								
Hepatitis C Serology								
HTLV-1 Serology								
VDRL								
EKG								
CT Scan /Chest/Abd/Pelvis				X				X
Bone Scan				X				X
Lymphocyte Subsets	X			X				X
Anti-TARP Antibody	X			X				X
NKT Cell Assessment								
Tetramer Staining	X	X	X	X	X	X		X
IFN-γ ELISPOT	X	X	X	X	X	X		X
 Cr CTL Assay#	X	X	X	X	X	X		X
PBMCs for Storage	X	X	X	X	X	X		X
Serum for Storage	X	X	X	X	X	X		X

Notes:

- Screening CT scans of the Chest/Abd/Pelvis and Bone Scans may be performed up to 8 weeks prior to enrollment and at outside institutions.
- All on study assessments can be obtained within +/- one week of scheduled measurement to allow for holidays and unscheduled delays.
- Screening for HLA-A\*0201 positivity will be completed before protocol eligibility screening is initiated. Only HLA-A\*0201 positive patients are brought to NIH for further screening and eligibility assessment.
- FluMist™ vaccination will be given with the seasonal influenza preparation when it is available at the time of enrollment.
- X\*: a 6th dose of TARP peptide vaccine will be administered to those patients with a ≥ 50% increase in PSADT at week 24 or who have confirmed immunologic responses to vaccination by tetramer or IFN-g ELISPOT assays as outlined in Section 5.2.1 Immunologic Response Criteria. A booster dose of TARP peptide vaccine will be administered to all patients at Week 48 and 96 who elect to continue on the extension phase of the study through Week 144..
- #: Cr CTL Assay will be performed at the time points indicated only in those patients with evidence of immunologic reactivity by tetramer staining and/or IFN-γ ELISPOT assays.

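### Section 5.1 ends AE reporting 30 days after the last dose: no scheduled visit follows a final booster within that window, and Sections 6.2 and 7 conflict with it on later non-serious events

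*Combined protocol and SAP*

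**What the plan says.** Section 5.1 (Data Collection) sets the reporting limit: "AEs should be reported up to 30 days following the last dose of study drug". The limit runs from a patient's last dose, so each patient has one closing date. Section 5.1 also follows AEs already identified until they resolve.

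Section 7 opens with a rule that has no end date: "At each study visit, patients will be evaluated for new or evolving AEs". Section 7.1.1 defines an AE by its timing relative to participation in the research, not relative to dosing. Section 6.2 tabulates all toxicities noted, by type and grade within arm, again without a time limit.

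Section 3.4.1 schedules clinical evaluation at "weeks 0, 3, 6, 9, 12, 15, 18, 24, 36, 48, 60, 72, 84, 96, 108, 120, 132 and 144", and Section 3.4.2 gives the same weeks for laboratory tests. On later doses, Section 3.1 says "Week 24 PSADT responders will be allowed to receive an additional dose of TARP peptide vaccine at Week 36" and "All patients will receive a booster of vaccine at Weeks 48 and 96". The notes to Appendix 1 restrict the week 48 and 96 boosters to patients "who elect to continue on the extension phase of the study through Week 144", so some men may have an earlier last dose.

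**The concern.** Safety and toxicity is a primary objective (Section 1.1.1), and Section 3.2 describes this as the first use of TARP vaccination in humans. Each of the five primary doses is followed by a visit with blood tests three weeks later, inside 30 days. A final booster is not. Staff will see the patient and ask about AEs at weeks 108, 120, 132 and 144, yet Section 5.1 read literally does not call for what they find to be reported.

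The stakes are the completeness of the toxicity table and its comparability between patients. Section 6.2 also compares grade distributions between arms once a toxicity appears in at least 5 patients on either arm, so the capture rule can decide whether that test is run. The risks named in Section 9.3.6 are not limited to the injection site: it lists transient transaminase rises and says "there is a chance for development of an autoimmune reaction to it", with possible prostate inflammation. Immune response is itself measured to week 144.

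**Working it through.** The plan gives no figure to reproduce. The check is calendar arithmetic.

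Inputs:
- Reporting window: 30 days after the last dose (Section 5.1).
- Visits: the weeks listed in Section 3.4.1.
- Doses: weeks 3, 6, 9, 12 and 15; week 36 for week 24 responders only; boosters at weeks 48 and 96 (Sections 3.1 and 5.2.1, Appendix 1).
- Visit allowance: 1 week either side (Section 5.1, Appendix 1).
- Permitted dose delay: up to 3 weeks (Section 5.1).

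Formulas: window closes at week (last dose + 30/7); gap in days = 7 × (next visit week − dose week).

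| Last dose | Window closes | Next visit | Gap | Visits after last dose and inside window |
|---|---|---|---|---|
| Week 15 | 15 + 4.3 = 19.3 | Week 18 | 21 days | Week 18 |
| Week 36 | 36 + 4.3 = 40.3 | Week 48 | 84 days | None |
| Week 48 | 48 + 4.3 = 52.3 | Week 60 | 84 days | None |
| Week 96 | 96 + 4.3 = 100.3 | Week 108 | 84 days | None |

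Most favourable permitted timing after a booster (dose 3 weeks late, next visit 1 week early): 84 − 21 − 7 = 56 days, still more than 30.

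Time outside the window after a week 96 dose: 144 − 100.3 = 43.7 weeks, and 43.7/144 = 30% of the study. Visits outside: weeks 108, 120, 132 and 144, which is all that remain.

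For a man who does receive the week 96 dose, the window stays open until week 100.3. His visits at weeks 48, 60, 72, 84 and 96 are therefore inside it, including the first visits after any week 36 dose and after the week 48 dose. Conversely, if his last dose was week 48, his window closed at week 52.3 and an event first found at week 60 or 72 falls outside. Whether such an event is in the window is known only once it is clear whether he is dosed again.

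Upper bound: a man last dosed at week 15 who stayed to week 144 would have 144 − 19.3 = 124.7 weeks outside. The documents do not describe this as a typical course, and he would have an in-window visit at week 18.

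**The case against.** The strongest reply is that other rules catch most of what matters, and much of it stands.

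- Section 7.3 sends every serious AE to the sponsor, with no 30-day limit.
- Section 7.2.2 lists for the IRB all related Grade 3-4 events, unexpected related Grade 2 events, all Grade 5 events and all serious events, also without a limit.
- Section 7.4.1 has all on-study laboratory data graded and reviewed, which includes weeks 108 to 144.
- The dose-limiting toxicity definition and the stopping rule carry no 30-day limit.
- A report card goes with every vaccine dose, and Section 3.4.1.4 checks injection sites at every clinical visit.

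A reader might infer that late events simply go unreported. These rules do not support that. Nor do they close the gap. The report card's daily grid covers days 1 to 5 and its scale grades injection-site reactions only (Appendix 6), so systemic and laboratory events rest on the visits. Related Grade 1 events, expected related Grade 2 events and unrelated non-serious events of any grade are outside Sections 7.2.2 and 7.3. For these, Section 5.1 points one way and Sections 6.2 and 7 the other.

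A reader might also infer that booster safety in general has no in-window visit. That holds only for the last dose a man receives. Finally, the documents name autoimmune reaction, prostate inflammation and granuloma without stating when they would arise, so a delayed onset cannot be attributed to them.

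How long to collect non-serious, unrelated AEs is a legitimate design choice. The objection here is that the plan states two incompatible choices.

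**Conclusion.** The point holds in limited form. After a final booster at week 96 (or at week 48 or 36 if dosing stops there), no scheduled clinical or laboratory assessment falls inside the reporting window: 84 days against 30, and never fewer than 56. After a week 96 dose, four visits and 43.7 weeks lie beyond it. The events at risk are non-serious ones, outside the Section 7.2.2 categories, first found at weeks 108 to 144 (or at the later visits of a man whose dosing stopped earlier). Their place in the primary safety tabulation is contradictory as written.

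This assumes that Section 5.1 means what it says, with one closing date counted from the last dose, and that patients attend only scheduled visits. The number of affected events cannot be estimated from the documents. It is an inexpensive correction to a primary-objective data rule, and does not show that serious late toxicity would be missed.

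**What to change.** Amend the reporting sentence in Section 5.1 to match Sections 6.2 and 7. Report all AEs through at least the first scheduled visit after the last dose (week 108 after a week 96 dose). After that, report all serious AEs and all AEs judged at least possibly related to vaccine, through the off-study or week 144 visit. A simpler alternative is to report all AEs to that visit. Section 6.2 should then state that the toxicity table uses the same period.

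The cost is some extra data entry and more unrelated events in the listings. The visits, AE questioning and laboratory tests are already scheduled. The change adds no assessment before week 108, so a transient laboratory abnormality after the final booster could still be missed; the safety report should state that limitation.
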